8.1 Collecting demographic information, medical history and concomitant medications

At the screening visit, information regarding medical history, concomitant medications and demographic information; i.e. age, ethnicity, BMI (calculated from height and weight measurements), previous smoking habits and physical activity (type and times/week) will be collected.

According to this information eligibility to participate in the study will be evaluated. Change in concomitant medications will re-evaluated at all study's visits.

8.2 Physical examination

Physical examination will be performed at screening visit, in order to evaluate eligibility to participate in the clinical study and eligibility to the surgery.

In addition physical examination of the surgery site will be evaluated at all studies' visits and will be used, inter alia, to assess AEs.

8.3 Subject's satisfaction questionnaire

Following laser assisted liposuction, subjects will be requested to scale their satisfaction from the treatment according to Subject's Satisfaction Questionnaire, based on 5 point Likert scale, as detailed in Table 2.

Subjects that underwent facial fat grafting procedure will be requested to fill in additional form, while referring to their satisfaction from the facial fat grafting procedure.

Table 2: Subject's Satisfaction Questionnaire- ALM-Lipo-002

Subject's Satisfaction Questionnaire

Procedure: Lower abdomen (w/wo flanks) / Outer thighs (w/wo inner thighs) / Facial fat grafting (*Please circle the relevant procedure*)

Subject Improvement and Satisfaction

1. Please rate your satisfaction from the treatment results

Subjects Improvement:

- 1- No Improvement
- 2- Mild Improvement
- 3- Moderate Improvement
- 4- Good Improvement
- 5- Excellent Improvement

Subjects Satisfaction:

- Very dissatisfied
- 2- Dissatisfied
- 3- Somewhat satisfied
- 4- Satisfied
- 5- Very satisfied

Satisfaction from skin reaction (tightening)

- 2. Please rate your satisfaction from the skin reaction (tightening) after the surgery
 - 1- Very dissatisfied
 - 2- Dissatisfied
 - 3- Somewhat satisfied
 - 4- Satisfied
 - 5- Very satisfied

Subject Personal Experience

- 3. Will you recommend the treatment to your family/friends?
 - 1- Extremely unlikely
 - 2- Very unlikely
 - 3- Somewhat unlikely
 - 4- Very likely
 - 5- Extremely likely

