8.4 Blinded digital photography evaluations

Standardized photography instructions

At Sanctuary Plastic Surgery Boca Raton FL,US

3D digital photographs will be taken using Canfield Scientific, Inc. camera, including;

- Lower abdomen w/wo flanks, without the face, for liposuction procedure evaluation

- Subject's face for facial fat grafting procedure evaluation.

At Assaf Harofeh Medical Center, Israel

2D and/or 3D digital photographs will be taken at Assaf Harofeh Medical Center. When using 2D camera (Nikon D7100), the camera will be placed at a distance of 2 meters from the subject. Only treated area will be photographed (i.e. lower abdomen w/wo flanks or thighs), without the face, at frontal, back, 45 degrees (left and right) and 90 degrees (left and right) positions, with arms resting on the side. In addition, for subjects that underwent facial fat grafting procedure, subject's face will be photographed at frontal, 45 and 90 degrees positions. Each position will be photograph 3 times.

Photographs will be taken at baseline and at 1, 3 and 6 months FU visits. The photographs will be downloaded to a computer under subject's identification number folder, and will be compiled into a PowerPoint presentation for panel evaluation.

Before and after photographs - Blinded evaluation

Panel of 3 physicians, blinded to the study design will evaluate the aesthetic outcomes of the treated area. The physicians will be presented with two photographs (baseline and 1/3/6 months after the surgery) and will be requested to assess which photograph represent the "before" (baseline) and which one the "after" (1/3/6 months after the surgery). In addition they will be requested to scale the improvement according to Global Aesthetic Improvement Scale (GAIS), as detailed in table 3.

Table 3: Global Aesthetic Improvement Scale (GAIS)- ALM-Lipo-002

Scale	Level of Improvement	
1	Very much improved	Optimal cosmetic results.
2	Much improved	Marked improvement in appearance, but not completely optimal.
3	Improved	Improvement in the appearance, better than initial condition, but re-treatment is advised.
4	No change	The appearance substantially remains the same compared to initial condition.
5	Worse	The appearance has worsened compared to the initial condition.

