9.2 Anticipated Outcome Related Adverse Events

Anticipated related AE for liposuction procedure may include; local pain, hematoma, contour deformities, infection, local fibrosis of scars or systemic side effects such as electrolyte disorders.

Anticipated related AE for facial fat grafting procedure may include; infection, ecchymosis, fat necrosis or injury of adjacent tissue.

Any anticipated AE that occurs at any time during or after the use of the study device must be reported by the Investigator to Alma Lasers Ltd. If the anticipated AE, in the

opinion of Alma Lasers or the Investigator, is likely to affect the safety of the subjects or the conduct of the study, the IRB/ Helsinki/ other ethic committee will be notified

of the effect within 10 working days after Alma Lasers first receives notice of it.

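### The satisfaction questionnaire's answer lists are unbalanced in different directions, and its improvement list has no level for worsening

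*Combined protocol and SAP*

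**What the plan says.** Subjects' satisfaction is a secondary objective (section 4.2). It is a secondary endpoint at 1, 3 and 6 months, separately for liposuction and facial fat grafting (section 5.1.2). The instrument is in section 8.3, Table 2, and Appendix A repeats it with the same labels, so the wording is not a slip in one table.

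- Item 1 has a single stem, "1. Please rate your satisfaction from the treatment results", followed by two answer lists. The improvement list runs from "1- No Improvement" to "5- Excellent Improvement". The satisfaction list goes from "2- Dissatisfied" straight to "3- Somewhat satisfied".
- Item 2, on skin tightening, uses the same satisfaction list.
- Item 3, on recommending the treatment, has "3- Somewhat unlikely" as its middle box. The next box up is already a strong likelihood.

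Elsewhere the protocol allows for a poor result. The panel's GAIS in section 8.4 has a lowest level described as "The appearance has worsened compared to the initial condition". Section 9.2 lists "local pain, hematoma, contour deformities, infection" among the anticipated events of liposuction.

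Section 10.1 makes all analyses descriptive: means and related statistics for continuous variables, counts and percentages for categorical ones. It does not say which of these applies to the questionnaire items, and no section gives a scoring rule or a cut-off for calling a subject satisfied.

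**The concern.** An answer that the form does not offer cannot be recovered at analysis. Three kinds of subject have no accurate box: one who looks worse (improvement list), one who is neutral (both satisfaction lists), and one who is mildly inclined to recommend (item 3).

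The design makes this matter more than it would in a controlled trial. The study is single-arm and open label, so no control group completes the same form, and a tilt in the labels passes straight into the reported result. The questionnaire is not given at baseline (section 7.2.2 and Table 1 in section 7.6), so change cannot be obtained by subtraction. The improvement list is the only subject-rated measure of change, and it stops at no improvement.

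At stake is how a satisfaction percentage from this study can be read, particularly if it is quoted as a single figure.

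**Working it through.** **Inputs.** Answer labels from Table 2 and Appendix A; GAIS levels from Table 3; 20 subjects, of whom 5 to 20 are to be eligible for facial grafting (section 6.1). The plan states no figure for satisfaction, so there is none to reproduce.

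**Step 1: count the labels.**

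| List | Negative | Neutral or no change | Positive |
|---|---|---|---|
| Improvement | 0 | 1 | 4 |
| Satisfaction with result | 2 | 0 | 3 |
| Satisfaction with skin tightening | 2 | 0 | 3 |
| Recommendation | 3 | 0 | 2 |
| Panel GAIS, for comparison | 1 | 1 | 3 |
| Balanced five-point list | 2 | 1 | 2 |

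None of the four subject lists matches the balanced pattern, and they do not depart from it in the same direction.

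**Step 2: what box 3 means.** Suppose all 20 subjects tick box 3 throughout. Each list then averages 3.0. By label, 20/20 = 100% report at least moderate improvement, 20/20 = 100% are at least somewhat satisfied, and 0/20 = 0% are likely to recommend. The same number carries different meanings, so only results by label can be interpreted.

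**Step 3: effect of the missing neutral on a satisfaction rate.** Let s be the share of truly neutral subjects. The documents give no value; I assume 10–40% and that all of them tick box 3.

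- Satisfied means 3 or more: added subjects = 20 × s, from 20 × 0.10 = 2 to 20 × 0.40 = 8, which is 10 to 40 percentage points.
- Satisfied means 4 or 5: added subjects = 0, because box 3 is not counted.

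If some neutral subjects tick box 2 instead, the first figure shrinks in proportion. One subject is worth 1/20 = 5 points in the full group and 1/5 = 20 points if only five subjects have grafting.

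**Step 4: effect of the missing worsening level.** If k of 20 subjects look worse, all k are merged into the no-improvement count and cannot be told apart from those who are unchanged. If a mean were reported and worsening would have scored one step lower, the mean is raised by k/20. For k = 1 to 4 (assumed), that is 0.05 to 0.20.

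**The case against.** The strongest reply is that the form still lets an unhappy subject say so. Such a subject can mark the two dissatisfied levels on both satisfaction lists and the lowest level on recommendation. Worsening has other routes as well: adverse events are assessed at each follow-up from the subject's report and examination (section 7.4), and the blinded panel can score GAIS 5. No mean score, pooled score, comparison across items or success threshold is planned. In a table of counts by label, a somewhat-satisfied answer is visible as such. The loose stem of item 1 is mainly layout, since two separately labelled lists follow it.

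Most of this stands, and it rules out several stronger readings that a reader might draw:

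- *That the questionnaire is biased upward as a whole.* The recommendation list leans the other way. On the satisfaction lists, the shift in Step 3 arises only if box 3 is counted as satisfied.
- *That the questionnaire cannot record a bad outcome.* This is true of the improvement list alone.
- *That the shares of positive boxes (4/5, 3/5 and 2/5) measure bias.* They count printed options and would be response rates only if subjects ticked at random.
- *That lack of comparability across items spoils a planned analysis.* None is planned; it is a reporting risk.

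The reply does not restore the missing answers. A panel score or an adverse event record is not the subject's own rating of change. Dissatisfaction is not the same as worsening, since a subject may be dissatisfied with a modest improvement. And because no cut-off is stated, nothing prevents box 3 from being counted as satisfied.

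**Conclusion.** The point holds in a limited form. The lists are unbalanced in different directions. The improvement list cannot separate worse from unchanged, the satisfaction lists give a neutral subject no accurate answer, and the recommendation list gives a mildly favourable subject none.

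The size depends on a rule that the plan leaves open. With a cut-off of 3 or more, the satisfaction rate would rise by 10–40 points, if 10–40% of subjects are neutral and all tick box 3. With 4 or 5 only, the shift by this route is zero. The neutral share and the number of worsened subjects are assumptions; the label counts come directly from the form.

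The effect is confined to secondary, descriptive endpoints. The primary endpoint, the blinded photographic comparison at 3 months, is unaffected. This is a cheap improvement that should be made, not a flaw that undermines the study.

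**What to change.** In both Table 2 and Appendix A:

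1. Relabel the midpoint of the satisfaction and skin-tightening lists *Neither satisfied nor dissatisfied*.
2. Relabel the midpoint of the recommendation list *Neither likely nor unlikely*.
3. Add a *Worse* level to the improvement list. This makes six levels, so either merge two of the improvement levels to keep five points, or change the five-point wording in the synopsis endpoints, section 5.1.2, Table 1 and section 8.3.
4. Split item 1 into 1a (improvement) and 1b (satisfaction), each with its own stem.

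In section 10, state that each item is reported separately as counts and percentages by label, and that satisfied means a score of 4 or 5.

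The cost is a revised form, an ethics submission at both sites, and the consequential edits in step 3. Comparability with any earlier use of the form would be lost, but the documents cite none. If follow-up has already begun, the reporting rule and the cut-off can still be fixed before analysis; answers that were never offered cannot be recovered.

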8.4 Blinded digital photography evaluations

Standardized photography instructions

At Sanctuary Plastic Surgery Boca Raton FL,US

3D digital photographs will be taken using Canfield Scientific, Inc. camera, including;

- Lower abdomen w/wo flanks, without the face, for liposuction procedure evaluation

- Subject's face for facial fat grafting procedure evaluation.

At Assaf Harofeh Medical Center, Israel

2D and/or 3D digital photographs will be taken at Assaf Harofeh Medical Center. When using 2D camera (Nikon D7100), the camera will be placed at a distance of 2 meters from the subject. Only treated area will be photographed (i.e. lower abdomen w/wo flanks or thighs), without the face, at frontal, back, 45 degrees (left and right) and 90 degrees (left and right) positions, with arms resting on the side. In addition, for subjects that underwent facial fat grafting procedure, subject's face will be photographed at frontal, 45 and 90 degrees positions. Each position will be photograph 3 times.

Photographs will be taken at baseline and at 1, 3 and 6 months FU visits. The photographs will be downloaded to a computer under subject's identification number folder, and will be compiled into a PowerPoint presentation for panel evaluation.

Before and after photographs - Blinded evaluation

Panel of 3 physicians, blinded to the study design will evaluate the aesthetic outcomes of the treated area. The physicians will be presented with two photographs (baseline and 1/3/6 months after the surgery) and will be requested to assess which photograph represent the "before" (baseline) and which one the "after" (1/3/6 months after the surgery). In addition they will be requested to scale the improvement according to Global Aesthetic Improvement Scale (GAIS), as detailed in table 3.

Table 3: Global Aesthetic Improvement Scale (GAIS)- ALM-Lipo-002

Scale	Level of Improvement	
1	Very much improved	Optimal cosmetic results.
2	Much improved	Marked improvement in appearance, but not completely optimal.
3	Improved	Improvement in the appearance, better than initial condition, but re-treatment is advised.
4	No change	The appearance substantially remains the same compared to initial condition.
5	Worse	The appearance has worsened compared to the initial condition.

8.5 Fat vitality assessment

Fat vitality assessment will be optional.

Ten (10) samples of the harvested fat, from 10 subjects at Assaf Harofeh MC, will be transported to the laboratory, within 4 hours.

Cell viability assessment will be performed using trypan blue exclusion assay.

9 Adverse Events (AE) and Serious Adverse Events (SAE)

The investigator is responsible for the detection and documentation of events meeting the criteria and definition of an adverse event (AE) or a serious adverse event (SAE) as provided in this protocol. During the study, when there is a safety evaluation, the investigator or site staff will be responsible for detecting AEs and SAEs, as detailed in this section of the protocol. All adverse events reported between consent and final follow-up will be recorded in the case report form (CRF).

9.1 Definition of an Adverse Event (AE)

Any untoward medical occurrence in a participant or clinical investigation participant, temporarily associated with the use of a medicinal product, whether or not considered related to the medicinal product.

An AE can therefore be any unfavourable and unintended sign (including an abnormal laboratory finding), symptom, or disease (new or exacerbated) temporally associated with the use of a medicinal product, whether or not considered related to the medicinal product. For marketed medicinal products, this also includes failure to produce benefits (i.e. lack of efficacy), abuse or misuse.

9.2 Anticipated Outcome Related Adverse Events

Anticipated related AE for liposuction procedure may include; local pain, hematoma, contour deformities, infection, local fibrosis of scars or systemic side effects such as electrolyte disorders.

Anticipated related AE for facial fat grafting procedure may include; infection, ecchymosis, fat necrosis or injury of adjacent tissue.

Any anticipated AE that occurs at any time during or after the use of the study device must be reported by the Investigator to Alma Lasers Ltd. If the anticipated AE, in the

opinion of Alma Lasers or the Investigator, is likely to affect the safety of the subjects or the conduct of the study, the IRB/ Helsinki/ other ethic committee will be notified

of the effect within 10 working days after Alma Lasers first receives notice of it.

9.3 Unanticipated Outcome Related Adverse Events

An unanticipated adverse device effect as defined by the Federal Regulations [21 CFR 812.3(s)] is "any serious adverse effect on health or safety or any life-threatening problem or death caused by, or associated with, a device, if that effect, problem, or death was not previously identified in nature, severity, or degree of incidence in the investigational plan or application (including a supplementary plan or application), or any other unanticipated serious problem associated with a device that relates to the rights, safety, or welfare of subjects." From a practical perspective, an unanticipated adverse device effect means a serious adverse event that is not listed in the device labelling, or the frequency or severity is greater than reported in the device labelling.

9.4 Definition of a Serious Adverse Event (SAE)

A serious adverse event is any untoward medical occurrence that, at any dose:

- a) Results in death
- b) Is life threatening
- Requires hospitalization or prolongation of an existing hospitalization.
 Hospitalization for elective treatment of a pre-existing condition that did not worsen from baseline is not considered an AE.
- d) Results in disability/incapacity
- e) Is a congenital abnormality / birth defect.
- f) Any event deemed by the investigator as being a significant medical event.

9.5 Recording of AEs and SAEs

When an AE/SAE occurs, it is the responsibility of the investigator to review all documentation (e.g. hospital progress notes, laboratory, and diagnostic reports) relative to the event. The investigator will then record all relevant information regarding an AE/SAE in to the CRF. It is not acceptable for the investigator to send photocopies of the subject's medical records to Alma Lasers Ltd. in lieu of completion of the appropriate AE/SAE CRF pages. However, there may be instances when copies of medical records for certain cases are requested by Alma Lasers Ltd. In this instance, all subject identifiers will be blinded on the copies of the medical records prior to submission to Alma Lasers Ltd.

For each adverse event, start and stop dates, action taken, outcome, intensity and relationship to study product (causality) must be documented. If an AE changes in frequency or intensity during a study, a new entry of the event must be made in the CRF.

The investigator will attempt to establish a diagnosis of the event based on signs, symptoms, and/or other clinical information. In the absence of a diagnosis, the individual signs/symptoms should be documented. All details of any treatments initiated due to the adverse event should be recorded in the subject's notes and the CRF.

9.6 Prompt Reporting of SAEs to Alma Lasers Ltd.

Once an investigator becomes aware that an SAE has occurred in a study subject, he/she will immediately notify the sponsor by contacting the study monitor via telephone to notify him/her of the event. The SAE form must be completed as thoroughly as possible with all available details of the event, signed by the investigator, and faxed within 24 hours of first becoming aware of the event to the following person:

[name]

Alma Lasers Ltd. [name]

[contact] [contact]

If the investigator does not have all information regarding an SAE, he/she will not wait to receive additional information before notifying the study monitor of the event and completing the form. The form will be updated when additional information is received.

The investigator must also notify the Reviewing IRB/ Helsinki/ other ethic Committee of any SAEs according to the guidelines of the Ethics Committee.

9.7 Evaluating AEs and SAEs

9.7.1 Assessment of Intensity

The investigator will make an assessment of intensity for each AE and SAE reported during the study. The assessment will be based on the investigator's clinical

judgement. The intensity of each AE and SAE recorded in the CRF should be assigned to one of the following categories:

Mild: An event that is easily tolerated by the subject, causing minimal discomfort and not interfering with everyday activities.

Moderate: An event that is sufficiently discomforting to interfere with normal everyday activities.

Severe: An event which is incapacitating and prevents normal everyday activities.

An AE that is assessed as severe should not be confused with an SAE. Severity is a category utilised for rating the intensity of an event; and both AEs and SAEs can be assessed as severe. An event is defined as "serious" when it meets one of the predefined outcomes as described in Section "Definition of an SAE".

9.7.2 Assessment of Causality

The investigator is obligated to assess the relationship between investigational device and the occurrence of each AE/SAE. The investigator will use clinical judgment to determine the relationship. Alternative causes, such as natural history of the underlying diseases, concomitant therapy, other risk factors, and the temporal relationship of the event to the investigational product will be considered and investigated. The investigator will also consult the IB and/or device information in the determination of his/her assessment.

The causal relationship to the study product assessed by the Investigator (or medically qualified delegate) should be assessed using the following classifications:

Not Related In the Investigator's opinion, there is not a causal relationship between the study product and the adverse event.

Unlikely The temporal association between the adverse event and study product is such that the study product is not likely to have any reasonable association with the adverse event.

Possible The adverse event could have been caused by the study participant's clinical state or the study product.

Probable The adverse event follows a reasonable temporal sequence from the time of study product administration, abates upon discontinuation of

the study product and cannot be reasonably explained by the known characteristics of the study participant's clinical state.

Definitely

The adverse event follows a reasonable temporal sequence from the time of study product administration or reappears when study product is reintroduced.

10 Statistical Analysis

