3.2.3 Procedure and parameters

Prior to performing the liposuction procedure, local anaesthesia is administered using the LipoFlow peristaltic mode. Tumescent fluid usage is 150 cc to 500 cc for a $10 \times 10 \text{ cm}^2$ area, while the anticipated total mg/kg dosage of tumescent lidocaine should not exceed 45 mg/kg.

Approximately 20–30 minutes should be allowed to enable an adequate diffusion of the tumescent solution and provide effective vasoconstriction.

Liposuction with the LipoLifeTM system involves simultaneous work of laser and suction. Alma 1470 diode laser is used in Continuous Wave (CW) emission mode, Pulse mode and Repeat mode. Power settings are recommended to be selected as a function of the liposuction area: 10-13W (chin, arms and knees), 13W (abdomen, back), and 15W (thighs, hips and buttocks). The laser energy is conveyed into the fat layer using a 3mm cannula which incorporates a 400 or $600\mu m$ optical single-use fiber. The suction tube is connected directly to the cannula so laser and suction will work simultaneously.

The LipoLifeTM system is designed to be operated only by licensed medical practitioners properly trained in its handling and use. Personnel operating the device must read the operator's manual.

4 Study Objectives

4.1 Primary objective:

To evaluate the efficacy of Laser Assisted Liposuction procedure with the LipoLife TM system.

4.2 Secondary objectives:

- To evaluate the efficacy of facial fat grafting procedure using autologous fat harvested with the LipoLifeTM system.
- To evaluate subjects' satisfaction.
- To evaluate procedure related safety.
- To evaluate fat vitality of the harvested fat with the LipoLifeTM system (optional).

5 Study Design

This is a multi-center, prospective, open label, single arm study.

The study will include 6 visits at the medical center: screening, pre-surgery evaluation visit, laser assisted liposuction surgery w/wo facial fat grafting and 3 follow up visits.

Following the screening visit, eligible subjects will be enrolled into the study. Each subject will undergo laser assisted liposuction surgery w/wo facial fat grafting (5-20 subjects), using the LipoLifeTM system. Pre-surgery evaluation visit will be carried out 1 week prior to the surgery. Follow up visits to evaluate safety and efficacy will take place at 1, 3 and 6 months after the surgery (See Figure 5 for an illustration of the study design).

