5.1.2 Secondary endpoints

 Improvement in aesthetic appearance as determined by blinded comparison of before and after 2D/3D digital photographs, at 1 and 6 months follow up visits

compared to baseline (2D or 3D at Assaf Harofeh MC ,Israel and 3D at Sanctuary Plastic Surgery, US).

[figure not shown]
- Improvement in facial aesthetic appearance in subjects that had a procedure of facial fat grafting, as determined by blinded comparison of before and after 2D/3D digital photographs at 1, 3 and 6 months follow up visits compared to baseline (2D or 3D at Assaf Harofeh MC, Israel and 3D at Sanctuary Plastic Surgery, US).
- Reduction in body weight measurement at 1, 3 and 6 months follow up visits compared to baseline.
- Reduction in abdominal fat thickness, among five (5) subjects that had a procedure
 of abdominal liposuction, as assessed by Magnetic Resonance Imaging (MRI) at 3
 months follow up visit compared to baseline. This test will be held at Sanctuary
 Plastic Surgery, US.
- Increase in facial fat volume, among five (5) subjects that had a procedure of facial fat grafting, as assessed by Magnetic Resonance Imaging (MRI) at 3 months follow up visit compared to baseline. This test will be held at the US site.
- Subject's satisfaction following liposuction procedure, as evaluated by subject's satisfaction questionnaire (based on 5 point Likert scale) at 1, 3 and 6 months follow up visits compared to baseline.
- Subject's satisfaction following facial fat grafting procedure, as evaluated by subject's satisfaction questionnaire (based on 5 point Likert scale) at 1, 3 and 6 months follow up visits.
- Safety endpoints will include adverse events (AE's) and serious adverse events (SAE's) occurring at any time during the trial or follow-ups.
- Fat vitality, as evaluated by cell viability assessment of 10 samples of the harvested fat (optional).

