7.3.2 Surgery Procedure

Perioperative antibiotic will be administered, per surgeon's discretion.

During the surgery, the study investigator, and/or his designee will perform laser assisted liposuction using the LipoLifeTM system, including:

- 1. Instilment of tumescent containing local anesthesia to the treated area (abdomen w/wo flanks or outer thighs (w/wo inner thighs), using the LipoFlow peristaltic mode.
- 2. Harvest of adipose tissue (1-3 liters) from the treated are, using the Lipoflow suction mode and LipoDiode CW mode.

The LipoLifeTM system is designed to be operated only by licensed medical practitioners properly trained in its handling and use. Personnel operating the device must read the operator's manual.

For facial fat grafting procedure (if relevant) the procedure will also include;

3. Injection of the harvested adipose tissue into the face, at least 5 cc per cheek, using the standard fat grafting equipment i.e. syringe, blunt cannula etc.

For fat vitality assessment (optional), ten (10) samples of the harvested fat, from 10 subjects at Assaf Harofeh MC, will be transported to the laboratory, within 4 hours. Cell viability assessment will be performed using trypan blue exclusion assay.

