10.3 Safety Analysis

A detailed list of all adverse events will be presented. The adverse event rate and incidence will be compiled with respect to frequency, nature, seriousness of the event, severity of the event, and relationship to the study device. In addition, listings of all safety measures will be produced.

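### Safety objective is procedure-related safety, but causality is rated and tabulated only against the device, so graft-injection events may be misclassified in the relatedness breakdown

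*Combined protocol and SAP*

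**What the plan says.** The synopsis and section 4.2 give the safety objective as "To evaluate procedure related safety". Section 5.1.2 sets a broad endpoint: "Safety endpoints will include adverse events (AE's) and serious adverse events", at any time in the trial, with no restriction by relatedness. Section 9.2 lists anticipated related events by procedure, with one list for liposuction and another for facial fat grafting.

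The provisions that produce relatedness data name a different object:

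- Section 9.5, on what must be recorded for each event: "intensity and relationship to study product (causality) must be documented".
- Section 9.7.2, on the assessment itself: "The investigator is obligated to assess the relationship between investigational device and the occurrence of each AE/SAE". All five categories are worded for the study product. The lowest says that "there is not a causal relationship between the study product and the adverse event". The middle one reads "The adverse event could have been caused by the study participant's clinical state or the study product".
- Section 10.3 compiles AE rate and incidence by frequency, nature, "seriousness of the event, severity of the event, and relationship to the study device". It also promises a full AE listing.

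On the graft injection, section 7.3.2 says that harvested fat is placed in the face "using the standard fat grafting equipment i.e. syringe, blunt cannula etc".

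**The concern.** The objective asks how safe the procedure is, while the only attribution collected asks whether the device caused the event. The two can differ when part of the operation is done without the device, and the facial injection is such a part.

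The plan has few other ways to separate procedural from incidental events. The study is single arm. AEs are recorded from consent to final follow-up (section 9), surgery may come up to 2 months after enrollment (7.1.3), and participation lasts up to 8 months (5.2). The overall AE rate therefore mixes pre-operative and unrelated events with procedural ones. Investigator attribution is the planned way to tell them apart, and it is asked about the device only.

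Consistency between sites is also at stake. All five US subjects are to be grafted, while grafting is optional in Israel (6.1). If the sites read the causality question differently, a difference in related events could reflect that reading and not the outcomes.

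**Working it through.** The documents state no AE rate and no figure on this point, so there is nothing to reproduce. The check is mainly one of text.

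**1. Is attribution to the procedure collected anywhere?** Sections 9.5, 9.7.2 and 10.3 use four terms: investigational device, investigational product, study product and study device. None is defined as including or excluding the liposuction surgery, the anaesthesia or the graft injection. No section adds a rating for any of these. The middle category of the scale offers only two sources, the subject's clinical state and the study product. An event caused by the injection itself fits neither.

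**2. Which events are exposed?** Set each part of the operation against the equipment used:

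- *Graft injection.* Standard syringe and blunt cannula (7.3.2), absent from the component lists in 3.2.1 and 3.2.2. Ecchymosis and injury of adjacent tissue, both anticipated in 9.2, can arise here, so a rating of not related to the device is defensible.
- *Graft infection and fat necrosis.* Less clear. LipoFlow is used for harvesting, filtering and transferring fat (3.1), and its components include a fat grafting sterile kit (3.2.2). An investigator could reasonably trace either event to the study system.
- *Liposuction.* Laser and suction are the study system (3.2.3), so many events would be rated device-related.
- *Tumescent anaesthesia.* Delivered through the LipoFlow peristaltic mode (3.2.3, 7.3.2), so a device rating is again plausible. Effects of the drug itself remain ambiguous.

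**3. Which way would the ratings err?** This cannot be determined. The equipment used for injection pulls towards not related. Two things pull the other way: section 9.2 already labels the listed events as related, and the highest category in 9.7.2 can be met by a reasonable temporal sequence alone, which many early postoperative events would satisfy.

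**4. How sensitive is a grafting-related rate?** The number grafted is 5 to 20 (section 5). Re-rating one subject's only related event changes the rate by 1/n:

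- n = 5: 1/5 = 20 percentage points
- n = 20: 1/20 = 5 percentage points

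To illustrate with an assumed single affected subject, take exact (Clopper-Pearson) 95% intervals. The lower limit is the 2.5% quantile of Beta(x, n − x + 1), set to 0 when x = 0. The upper limit is the 97.5% quantile of Beta(x + 1, n − x).

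| Grafted | Rated related | Rated not related |
|---|---|---|
| 5 | 1/5 = 20% (0.5% to 71.6%) | 0/5 = 0% (0% to 52.2%) |
| 20 | 1/20 = 5% (0.1% to 24.9%) | 0/20 = 0% (0% to 16.8%) |

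The counts are assumed. The table shows sensitivity to one rating and does not predict bias.

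**The case against.** The strongest reply is that nothing is lost. The endpoint is all AEs and SAEs, relatedness is only one of five breakdowns in 10.3, every event is listed, and no headline related-event rate is planned. This stands, and it limits the point to the relatedness breakdown.

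A second reply is that the documents treat grafting as use of the study system. The synopsis says the system will be used for both liposuction and facial grafting, and LipoFlow's vacuum mode serves fat transplant procedures (3.2.2). This stands for harvesting and transfer. It does not cover the final injection in 7.3.2.

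A third reply is that attribution could be rebuilt afterwards. With about 20 subjects, and with grafting in the face and liposuction in the abdomen or thighs, the nature and site of most local events would show which procedure was involved. This stands in part. Systemic events and anaesthetic effects would remain ambiguous, and the result would be a retrospective judgement in place of the investigator's rating at the time.

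A reader might infer that grafting events would vanish from the safety results, or that their related rate would be near zero by construction. The documents support neither. The events stay in the overall rate and the listing, the study system takes part in preparing the graft, and the scale is loose enough for over-attribution to be as plausible as under-attribution.

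**Conclusion.** The mismatch is real. The objective concerns the procedure, while the recorded causality item, the rating scale and the relatedness breakdown concern only an undefined device or product. The effect is misclassification of uncertain direction in that breakdown. It is clearest for injection injuries such as ecchymosis and adjacent-tissue damage, and weaker for graft infection, fat necrosis, liposuction and tumescent events.

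Its size cannot be stated, because the documents give no AE rates. All that follows from the planned numbers is that each re-rated subject moves a grafting-related rate by 5 points (20 grafted) to 20 points (5 grafted). The conclusion rests on reading the device terms in their ordinary sense, since the protocol does not define them.

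Safety is a secondary objective with descriptive analysis (10.1), and the primary endpoint is unaffected. The change is still worth making before data collection, because as written the relatedness breakdown does not answer the stated objective.

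**What to change.** In sections 9.5 and 9.7.2 and on the AE CRF, rate causality separately for:

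1. the LipoLife device;
2. the liposuction procedure, including tumescent anaesthesia;
3. the facial fat grafting procedure, where done.

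Use one defined term for the device throughout, and word the categories so that each can be applied to all three.

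In section 10.3, add a procedure-related AE table beside the device-related breakdown. Report liposuction-related events over all operated subjects and grafting-related events over subjects actually grafted.

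The cost is two extra CRF fields per event and one extra table. The reported related-AE rate may be higher than a device-only rate. A smaller change would be to define the study product as including the procedure. That would make ratings more uniform, but it would merge device and procedure, so neither could be reported separately.
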